12.1 Inclusion Criteria

To be eligible for randomization in this study, a subject must fulfill ALL of the following criteria:

1. Written and signed informed consent must be obtained before any protocol specific assessment is performed.
2. Male or female, aged 18 years or older
3. Has at least 3 of the following symptoms:
 - Cough
 - Production of purulent sputum
 - Dyspnea (shortness of breath)
 - Pleuritic chest pain.
4. Has at least TWO of the following abnormal vital signs
 - Fever or hypothermia documented by the investigator (temperature $> 38.0^{\circ}\text{C}$ [100.4°F] or $< 36.0^{\circ}\text{C}$ [95.5°F])
 - Hypotension with systolic blood pressure (SBP) < 90 mm Hg
 - Heart rate > 90 bpm
 - Respiratory rate (RR) > 20 breaths/minute.
5. Has at least 1 clinical sign or laboratory finding associated with CABP:
 - Hypoxemia (partial pressure of arterial oxygen [PaO_2] < 60 mm Hg by arterial blood gas [ABG] or oxygen saturation $< 90\%$ by pulse oximetry)
 - Physical examination findings of pulmonary consolidation (eg, dullness on percussion, bronchial breath sounds, or egophony)
 - An elevated total white blood cell (WBC) count ($> 12,000$ cells/ mm^3) *or* leucopenia ($\text{WBC} < 4,000$ cells/ mm^3) *or* elevated immature neutrophils ($> 15\%$ band forms, see % bands calculation in [Appendix 4](#), regardless of total peripheral WBC count).
6. Radiographically-confirmed pneumonia, ie, new or progressive pulmonary infiltrate(s) on chest X-ray (CXR) or chest computed tomography (CT) scan consistent with acute bacterial pneumonia within 24 hours prior to the first dose of test article.
7. Has disease categorized as being PORT Risk Class II, III, or IV at Screening (see PORT Risk Class calculation in [Appendix 2](#)).
8. Is expected to require a minimum of at least 3 days of iv therapy for the initial treatment of CABP.
9. Females must have a negative urine pregnancy test at Screening and agree to comply with using an acceptable method of birth control as per your local requirements (eg, abstinence, po contraceptive, intrauterine device [IUD], barrier contraception [condom], tubal ligation, hysterectomy, bilateral oophorectomy, postmenopausal or vasectomized partner) from Screening through post therapy evaluation (PTE). Males must agree to use an acceptable method of birth control with female partner(s) and must not donate sperm from Screening through PTE.

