22.6 Analysis of Additional Efficacy Variables

Additional efficacy analyses will be conducted to support the efficacy findings of the primary and secondary outcomes. CIs will be determined for descriptive purposes, but no conclusions of NI will be made.

The number and percentage of subjects classified as a Clinical Success, Clinical Failure and Indeterminate by the Investigator's Assessment at EOT in the ITT and CE populations (by definition subjects with an Indeterminate response are excluded from the CE population) will be calculated. A 2-sided unadjusted 95% CI will be constructed for the observed difference in the Clinical Success rate using the method of Miettinen and Nurminen ([Miettinen and Nurminen, 1985](#)).

The number and percentage of subjects with stabilization of vital signs and clinical signs/laboratory findings associated with CABP at 72-120 hours post first dose of test article will be presented by treatment group in the ITT population. These include body temperature (no fever or hypothermia), SBP (> 90 mm Hg), heart rate (< 90 bpm), RR (< 20 breaths/minute), PaO₂ (≥ 60 mm Hg by ABG or oxygen saturation $\geq 90\%$ by pulse oximetry), physical exam findings (no findings of pulmonary consolidation), WBC count ($< 12,000$ cells/mm³ or $\geq 4,000$ cells/mm³) or immature neutrophils ($< 15\%$).

A summary (number and percentage of subjects) of the assessment of clinical signs and symptoms of CABP at each time point throughout the study will be presented by treatment group in the ITT population. The number and percentage of subjects with resolution of signs and symptoms present at Screening (back to pre-CABP status) will also be provided by study visit. The number and percentage of subjects with no worsening of clinical symptoms of CABP and with the absence of new symptoms of CABP will also be provided by treatment group in the ITT population.

The per-subject and per-pathogen microbiologic outcomes will be provided for the microITT and ME populations at the EOT and PTE visits. Two-sided unadjusted 95% CIs will be provided for the difference in per-subject microbiological favorable outcome rates.

A concordance analysis of Early Clinical Response and Investigator's Assessment of Clinical Response at PTE in the ITT analysis set will also be presented.

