6 STUDY POPULATIONS

6.1 Analysis Populations

6.1.1 Intent-to-Treat (ITT) Population

The ITT population will consist of all randomized subjects regardless of whether or not the subject received test article. A subject is considered randomized when the IxRS provides the test article assignment (ie, completes a randomization transaction).

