10.4 Additional Analyses

Additional efficacy analyses will be conducted to support the efficacy findings of the primary and secondary outcomes. CIs will be determined for descriptive purposes, but no conclusions of NI will be made.

Clinical Outcomes

The number and percentage of subjects classified as a Clinical Success, Clinical Failure, and Indeterminate by the Investigator's Assessment at EOT in the ITT and CE-EOT populations (by definition subjects with an Indeterminate response are excluded from the CE-EOT population) will be calculated. The number and percentage of subjects in each response category for the overall assessment of Clinical response at PTE (based on the investigator's assessment) in the microITT population will also be provided. Two-sided unadjusted 95% CIs will be constructed for the observed difference in the Clinical Success rate using the method of Miettinen and Nurminen (1985).

The number and percentage of subjects with stabilization of all vital signs associated with CABP at 72 to 120 hours post first dose of test article will be presented by treatment group in the ITT population as will the number and percentage of subjects with stabilization of each vital sign. These include temperature (no fever or hypothermia), SBP (> 90 mmHg), heart rate (< 90 bpm), RR (< 20 breaths/minutes), and PaO₂ (> 60 mmHg by pulse oximetry or ABG). WBC count ($< 12,000$ cells/mm³ or $\geq 4,000$ cells/mm³) and immature neutrophils ($< 15\%$).

A summary (number and percentage of subjects) of the assessment of clinical symptoms of CABP at each time point throughout the study will be presented by treatment group in the ITT population. Clinical symptoms of CABP (cough, pleuritic chest pain, dyspnea, and phlegm/sputum production) will be summarized as shift tables of score (absent, mild, moderate, and severe) as compared with baseline. Percentages for clinical symptoms will be based on the number of subjects with a baseline and post-baseline evaluation at the time point of the specific clinical symptom. The number and percentage of subjects with resolution of all symptoms present at baseline (back to pre-CABP status) will also be provided by study visit in the ITT population. The number and percentage of subjects with no worsening of clinical symptoms of CABP and with the absence of new symptoms of CABP will also be provided by treatment group and study visit in the ITT population.

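### The per-sign 'stabilisation' rows in SAP 10.4 mix subjects who recovered with subjects never abnormal on that sign; this matters mainly for systolic pressure and partly for temperature

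*Combined protocol and SAP*

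**What the plan says.** SAP 10.4 (Clinical Outcomes) gives the number and percentage of subjects with stabilisation of all vital signs at 72 to 120 hours, "as will the number and percentage of subjects with stabilization of each vital sign". The limits are no fever or hypothermia, "SBP (> 90 mmHg), heart rate (< 90 bpm), RR (< 20 breaths/minutes"), and a PaO2 limit. The results are those "post first dose of test article will be presented by treatment group in the ITT population", and SAP 6.1.1 defines that population: "The ITT population will consist of all randomized subjects regardless of whether or not the subject received test article".

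Inclusion Criterion 4 (protocol version 2.0, section 12.1) reads "Has at least TWO of the following abnormal vital signs". The four signs are temperature, systolic pressure, heart rate and respiratory rate. The entry cut-offs mirror the later limits: for example "Hypotension with systolic blood pressure (SBP) < 90 mm Hg" and "Heart rate > 90 bpm". Hypoxemia is only one of three alternatives in Criterion 5.

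Protocol section 22.6 plans the same summary ("The number and percentage of subjects with stabilization of vital signs and clinical signs/laboratory findings associated with CABP at 72-120 hours post first dose") and also sets no baseline condition. SAP 8.3 takes subjects with missing data out of denominators, but not subjects who were normal at baseline. The symptom analysis in the next paragraph of SAP 10.4 does refer to baseline: it uses shift tables and counts resolution of the symptoms that were present then.

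**The concern.** Stabilisation suggests that something unstable became stable. As specified, a subject with a systolic pressure of 130 at entry and 128 at 96 hours counts as stabilised on that sign. An eligible subject may be normal on up to two of the four signs, so each row adds a recovery rate to a share that reflects who was enrolled.

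SAP 10.4 presents these analyses as support for the primary and secondary efficacy findings. A row close to its ceiling in both arms could be read as evidence of similar efficacy when it says little about treatment. The mixing also dilutes any between-arm difference in recovery, whichever arm is better.

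**Working it through.** The plan states no rate, N or power for these rows, so there is no figure of its own to reproduce.

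**Algebra.** Let q be the share normal on a sign at entry, s the share of those within limits at 72–120 h, and r the share of entry-abnormal subjects within limits at 72–120 h.

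- Reported rate = qs + (1−q)r. If all normal subjects stay normal (s = 1), this is q + (1−q)r.
- A between-arm difference d in r, with s equal in both arms, shows as (1−q)d.
- Example: q = 50% and r = 30% give 0.50 + 0.50 × 0.30 = 65%. A 10-point difference shows as 5.0 points. At q = 95% it shows as 0.5 points.

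**Bound from the entry rule.** With at least two of four signs abnormal in every eligible subject, q averaged over the four signs is at most 2/4 = 50%. If systolic pressure is normal in 95%, the other three average at most (2 − 0.95)/3 = 35%. The rows therefore cannot all be heavily inflated.

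**Size by sign.** The documents give neither prevalence nor variability by sign, so everything below is assumed. I simulated 1,000,000 candidates with underlying means of 38.0 °C, 125 mmHg, 98 bpm and 22/min, between-subject SD 0.8/18/14/3.5 and within-subject SD 0.4/7/7/2. Subjects with at least two abnormal first readings were kept. The second reading had the same underlying value and fresh noise, so there was no change in clinical state.

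| Sign | Abnormal at entry (1−q) | s | r | Reported rate | Points from entry-normal (qs) |
|---|---|---|---|---|---|
| Temperature | 66.0% | 77.5% | 21.5% | 40.5% | 26.4 |
| Systolic pressure | 4.7% | 98.4% | 44.0% | 95.9% | 93.8 |
| Heart rate | 84.1% | 70.4% | 12.9% | 22.0% | 11.2 |
| Respiratory rate | 83.6% | 67.4% | 14.5% | 23.1% | 11.0 |

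Check for temperature: 0.340 × 77.5 + 0.660 × 21.5 = 26.4 + 14.2, about 40.5.

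Milder means (37.6/128/94/21) and sicker means (38.3/118/104/24) give reported rates of 32–53% for temperature, 92–97% for systolic pressure, 15–26% for heart rate and 13–28% for respiratory rate. Rounding readings to 0.1 °C and whole units changes the central values to 42, 96, 20 and 19%.

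**Dilution.** In the central case a 10-point difference among entry-abnormal subjects shows as 0.660 × 10 = 6.6 points (temperature), 0.047 × 10 = 0.5 (systolic pressure), and 8.4 for both heart rate and respiratory rate.

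**Second method.** Assume instead independent abnormality of temperature/systolic pressure/heart rate/respiratory rate at 40/2/60/50%, 60/5/80/70% or 80/15/95/90%, conditional on at least two abnormal. With s = 1 and r = 0 the reported rate equals q: 85–97% for systolic pressure, 18–37% for temperature, 8–25% for respiratory rate and 4–17% for heart rate. The ordering is the same.

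**The case against.** **The share within limits at a fixed time is a legitimate summary.** The oral-switch criteria in protocol section 14.3.1.2 define clinical stability by thresholds without requiring an earlier abnormality. This stands, and it is why the ITT row should stay under a label that says what it measures.

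**Entry-normal subjects are not automatic responders.** A reader might infer that they always count as stabilised and carry no information on treatment. The documents do not support that. Such subjects can become febrile, hypotensive or tachycardic, and protocol section 9.1 reports transient heart-rate increases on omadacycline. Values of exactly 90 mmHg, 90 bpm or 20/min are normal at entry but outside the later limits. In the central simulation about 67–98% of entry-normal subjects count, depending on the sign. Replacing the ITT row would hide deterioration among them.

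**Much of the low-level rate has another cause.** For heart rate and respiratory rate about half of the no-change rate is regression to the mean among entry-abnormal subjects. Conditioning on baseline leaves that in place: r is 21.5, 44.0, 12.9 and 14.5% in the table. This also stands. Randomisation should make it similar in both arms.

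**Nothing is decided on these rows.** A reader might infer that the non-inferiority conclusion is biased. SAP 10.4 says no such conclusion will be drawn from its analyses, and the primary test in SAP 10.1 uses Early Clinical Response.

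**Context is already planned.** SAP 9.2 tabulates the baseline abnormalities by arm, SAP 11.2 summarises change from baseline in vital signs, and SAP 8.1 provides listings. A careful reader could see that q is large for systolic pressure, but these tables do not give recovery among abnormal subjects.

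**Conclusion.** The point holds as a minor defect of definition and labelling. The per-sign ITT rows do not separate recovery from never having been abnormal, and neither protocol section 22.6 nor SAP 8.3 corrects this. The algebra is exact under its stated conditions, but the sizes rest on assumed prevalence and variability. Under those assumptions the systolic pressure row reads about 92–97% with no change in state and is nearly uninformative about treatment. Temperature is materially affected (about 32–53%), and heart rate and respiratory rate only modestly.

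It would go too far to say that all rows show high rates without a treatment effect: that description fits systolic pressure and, in part, temperature. The all-signs row is not inflated by never-abnormal subjects, because every eligible subject has at least two abnormal signs at entry. The effect is dilution of any difference in recovery, not bias towards one arm.

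**What to change.** In SAP 10.4, for each vital sign, add by arm the number and percentage within limits at 72–120 h among ITT subjects who were abnormal on that sign by the Inclusion Criterion 4 cut-off, and show that N. State that abnormality is judged on the Screening value that established eligibility. Under SAP 8.2 baseline is the last value before dosing, and a subject who qualified at Screening but was normal just before the first dose would otherwise drop out. If the PaO2 row is kept among the vital signs, use the Criterion 5 cut-off for it.

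Keep the existing ITT row for each sign, but label it 'within limits at 72–120 h', so that worsening in baseline-normal subjects stays visible. Leave the all-signs row as it is.

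No new data are needed, since the vital signs are already scheduled. The cost is a change of SAP wording, one more set of table rows and a small N for systolic pressure. That small N is the actual amount of information on recovery from hypotension, which the ITT denominator conceals.

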7 CHANGES IN CONDUCT OR PLANNED ANALYSES FROM THE PROTOCOL

The expanded microITT population was added and selected analyses are conducted in this population.

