A table will provide the frequency counts and percentages by treatment group for subjects who received prior antibiotics (as randomized), PORT Risk Class (from the eCRF and as randomized), CURB-65 Score, subjects meeting the modified American Thoracic Society (ATS) severity criteria, and subjects meeting the SIRS criteria for the ITT, microITT and CE-PTE populations. PORT score will also be summarized as a continuous variable. CURB-65 score is derived from the eCRF data and ranges from 0-5 where 1 point is given for each of the following at baseline: confusion, blood urea nitrogen > 19 mg/dL (urea > 6.8 mmol/L), respiratory rate \geq 30 breaths/min, systolic blood pressure < 90 mmHg or diastolic blood pressure \leq 60 mmHg, and age \geq 65 years. Confusion is defined as altered mental status as recorded on the PORT Risk Class Determination eCRF. Modified ATS severity and SIRS criteria are derived from the eCRF data. Modified ATS severity criteria is defined as presence of \geq 3 of the following 9 criteria at baseline: respiratory rate \geq 30 breaths/min, O₂ saturation < 90% or PaO₂ < 60 mmHg, urea \geq 20 mg/dL, WBC < 4000 cells/mm³, confusion, multilobar infiltrates, platelets < 100,000 cells/mm³, temperature < 36°C, and systolic blood pressure < 90 mmHg. SIRS criteria is defined as having 2 or more of the following 4 symptoms at baseline: temperature < 36°C or > 38°C (oral or oral equivalent), heart rate > 90 bpm, respiratory rate > 20 breaths/min, WBC < 4000 cells/mm³ or WBC > 12,000 cells/mm³, or bands > 10%. Differences between treatment groups will be tested using Fisher's exact test for categorical variables and the Wilcoxon rank sum test for continuous variables.

By-subject listings of the modified ATS severity criteria and SIRS criteria will be provided. A listing of subjects with discrepancies between the PORT Risk Class to which they were randomized and their true PORT Risk class as captured in the clinical database will also be provided.

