Baseline assessments of clinical symptoms, clinical signs, abnormal vital signs, and abnormal laboratory signs of CABP will be presented for the ITT, Safety, microITT, and CE-PTE populations. The number and percentage of subjects with each of the CABP symptoms (cough, pleuritic chest pain, dyspnea, and phlegm/sputum production) by severity (absent, mild, moderate, severe) will be presented by treatment group. The number and percentage of subjects with the presence by severity (ie, absent, mild, moderate, severe) of the following clinical signs will be provided by treatment group: rales, rhonchi, dullness on percussion, bronchial breath sounds, wheezing, decreased breath sounds, and egophony. The number

and percentage of subjects with fever (defined as body temperature $> 38^{\circ}\text{C}$ [100.4°F] oral or rectal), hypothermia (defined as body temperature $< 36^{\circ}\text{C}$ [95.5°F] oral or rectal), hypotension with systolic blood pressure $< 90 \text{ mmHg}$, heart rate $> 90 \text{ bpm}$, respiratory rate $> 20 \text{ breaths/min}$, hypoxemia (defined as $\text{PaO}_2 < 60 \text{ mmHg}$ by arterial blood gas or oxygen saturation $< 90\%$ by pulse oximetry), elevated total WBC count ($> 12,000 \text{ cells/mm}^3$), leucopenia (WBC $< 4,000 \text{ cells/mm}^3$), elevated immature neutrophils ($> 15\%$ band forms regardless of total peripheral WBC count) and any of elevated total WBC count, leucopenia or elevated immature neutrophils will be summarized by treatment group. Differences between treatment groups will be tested for statistical significance using Fisher's exact test.

Risk factors for CABP will be presented by treatment group for the ITT, Safety, microITT, and CE-PTE populations. Risk factors include smoking (current, past, and descriptive statistics of the number of years since quitting for those subjects who were previous smokers), receipt of pneumococcal vaccine, prior lung infection, whether the subject had mild to moderate COPD, symptomatic asthma with wheezing, and chronic cough with or without sputum production. Differences between treatment groups will be tested for statistical significance using Fisher's exact test for categorical variables and the Wilcoxon rank sum test for continuous variables. Other medical and surgical history will be summarized based on MedDRA system organ class by treatment group for the ITT and Safety populations.

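### SAP 10.4's 72–120 hour stabilisation table uses a WBC rule that no value can fail and a mmHg cutoff for pulse oximetry that conflicts with protocol v2.0 section 22.6 and SAP 9.2

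*Combined protocol and SAP*

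**What the plan says.** SAP section 10.4 (Clinical Outcomes) plans counts and percentages, by arm in the ITT population, of subjects with "stabilization of all vital signs associated with CABP" at 72 to 120 hours, and the same for each vital sign. The listed criteria are temperature, SBP > 90 mmHg, heart rate < 90 bpm, respiratory rate < 20 breaths/minute and PaO2 > 60 mmHg. The text then runs "mmHg by pulse oximetry or ABG). WBC count". The white-cell rule that follows is < 12,000 *or* ≥ 4,000 cells/mm³, with immature neutrophils < 15%. These last two items stand after a full stop, in a fragment without a verb. Section 10.4 is descriptive and rules out any non-inferiority conclusion.

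Protocol v2.0 section 22.6 describes the parent analysis as "stabilization of vital signs and clinical signs/laboratory findings associated with CABP". It has the same *or* in the WBC rule, as did v1.0. Its oxygenation rule is PaO2 ≥ 60 "mm Hg by ABG or oxygen saturation" ≥ 90% by pulse oximetry. It also includes "physical exam findings (no findings of pulmonary consolidation"), which SAP 10.4 does not list.

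SAP section 9.2 uses a 90% saturation limit twice at baseline: in the modified ATS criteria ("saturation < 90% or PaO"2 < 60 mmHg) and in the hypoxemia definition (PaO2 < 60 mmHg "by arterial blood gas or oxygen saturation" < 90%). It treats WBC as abnormal when > 12,000 or < 4,000.

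SAP section 7 lists one change from the protocol: "The expanded microITT population was added and selected analyses are conducted in this population".

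**The concern.** A stabilisation criterion has to be capable of being failed. The WBC rule is not: counts of 1,000 and 30,000, both abnormal under SAP 9.2, would be tabulated as stable. The oxygenation rule attaches a partial pressure to a device that the documents elsewhere pair with a saturation percentage. A programmer would have to guess what to do with an oximetry reading. Oxygenation is listed among the vital signs, so the guess would also enter the composite.

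At stake is the usefulness of one table that covers the same 72–120 hour window as Early Clinical Response and is meant to support it. Programmed as written, its WBC result cannot show a difference between arms in either direction.

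**Working it through.** The plan states no figure for this table, so there is none to reproduce. The check applies the rules as written.

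**1. WBC.** Inputs: the rule in SAP 10.4 and protocol 22.6, and the abnormality limits in SAP 9.2. The sets {x < 12,000} and {x ≥ 4,000} together cover all values.

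| WBC (cells/mm³) | Abnormal in SAP 9.2 | Stable with *or* | Stable with *and* |
|---|---|---|---|
| 1,000 | yes | yes | no |
| 3,999 | yes | yes | no |
| 4,000 | no | yes | yes |
| 11,999 | no | yes | yes |
| 12,000 | no | yes | no |
| 12,001 | yes | yes | no |
| 30,000 | yes | yes | no |

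Over every integer from 0 to 200,000, the *or* rule fails 0 of 200,001 values. With *and*, 4,000 values fail at the low end (0 to 3,999) and 188,001 at the high end (12,000 to 200,000), 192,001 in all. The opposite of an *either too high or too low* definition needs *and*.

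The value 12,000 is neither abnormal in SAP 9.2 nor stable under < 12,000. The same gap exists at SBP 90, heart rate 90 and respiratory rate 20. It is a convention of the table and a separate matter from the operator.

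**2. What the *or* hides.** If a share f of subjects with a value is out of range, the corrected row is 100 × (1 − f), against 100 as written. The difference between arms is 100 × (f_moxifloxacin − f_omadacycline), against 0 as written. The documents give no f. Purely as an assumption, f from 5% to 30% would give rows from 95% down to 70%.

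**3. Oxygenation.**

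| Source | ABG | Pulse oximetry |
|---|---|---|
| Protocol v1.0, 22.6 | PaO2 > 60 | not used |
| Protocol v2.0, 22.6 | PaO2 ≥ 60 | saturation ≥ 90% |
| SAP 9.2 (hypoxemia) | PaO2 < 60 | saturation < 90% |
| SAP 10.4 | PaO2 > 60 | PaO2 > 60 mmHg |

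The protocol v2.0 rule is the exact complement of SAP 9.2. SAP 10.4 is not: a PaO2 of exactly 60 is stable in the protocol and not stable in the SAP. If the number 60 were applied to a saturation reading, 61% to 89% (89 − 61 + 1 = 29 whole-number values) would be stable in SAP 10.4 but hypoxemic in SAP 9.2.

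The strict > 60 is the v1.0 limit, although the SAP (17 March 2017) postdates protocol v2.0 (27 October 2015). Other v1.0 text survives in the SAP: section 6.1.4.1 quotes inclusion criterion 5 with ABG only, and the Appendix 1 schedule lists ABG only. An incomplete carry-over is the likeliest explanation.

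**4. Data in the window.**
- WBC is scheduled centrally at Day 4 (protocol 16.1.3).
- ABG or oximetry is scheduled at Screening only (v2.0 flowchart). Vital signs are temperature, BP, heart rate and respiratory rate (footnote n). Later saturation or PaO2 is described only among the oral-switch criteria (14.3.1.2).
- The central differential in Table 5 has no band count, and routine local samples are planned at Screening only (16.1.3).

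**The case against.** The strongest reply is that this is one descriptive table, that the WBC *or* is the protocol's own wording, and that any programmer would see what was meant. The protocol also says the SAP will come with mock table shells, which are not in the documents reviewed and might settle the rows. One could further read each WBC limit as applying only to subjects abnormal in that direction at baseline.

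The limited reach stands. Inheritance explains the *or* but does not make it workable, and the baseline-direction reading is not written anywhere. Because WBC sits in a fragment and is not a vital sign, it may not get its own row or enter the composite. The conclusion is therefore stated for any row or component that uses the rule.

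A second objection also stands: editing words does not supply data. With no routine post-Screening saturation or band count described, a correctly worded rule may still rest on a selected subset. The fix has to deal with that.

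A reader might infer that SAP section 7 conceals a change to the WBC rule. It does not, since the SAP and protocol agree on that wording. Section 7's silence bears only on the oxygenation departure and on the narrower scope, including the missing consolidation component.

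**Conclusion.** Two errors stand on the text alone: a WBC criterion that every value satisfies, and an oximetry criterion in the wrong unit that conflicts with protocol v2.0 section 22.6 and SAP 9.2. The first gives 100% in both arms among subjects with a value, by logic and without any assumption.

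Severity is minor. The table is descriptive, and Early Clinical Response, its non-inferiority test, alpha and power do not use it. WBC is also summarised by visit, including Day 4 [+1 day], and in graded shift tables (SAP 11.4), so the data are not lost.

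Three stronger readings are not supported. The documents do not show that a real difference between arms will be hidden, because they give no out-of-range share at 72–120 hours; the 5% to 30% range above is illustration only. They give no count of subjects affected by the oxygenation wording. And they do not suggest a deliberate loosening of the oxygenation standard, since > 60 is slightly stricter than ≥ 60 for ABG and the text looks like a partial update.

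**What to change.** In SAP section 10.4:
- Write the WBC rule as ≥ 4,000 *and* < 12,000 cells/mm³.
- Use the protocol v2.0 section 22.6 oxygenation rule: PaO2 ≥ 60 mm Hg by ABG, or oxygen saturation ≥ 90% by pulse oximetry.
- Report the oxygenation and immature-neutrophil rows only among subjects with a value in the window, and print the denominator by arm. SAP 8.3 already provides for reduced denominators; here they need to be visible.

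In SAP section 7:
- Declare the change from *or* to *and* in the WBC rule, because it departs from the protocol's literal text.
- Declare that the pulmonary-consolidation component has been left out. Restoring it is not asked for: after Screening, examination changes are recorded as AEs (v2.0 flowchart footnote m), so no structured status at 72–120 hours is described.

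The cost is a few words in section 10.4, a denominator column and a short entry in section 7, using thresholds already in the documents. These edits do not make saturation or band counts available where they were not collected; the denominators will show how far those rows can be relied on.
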